4.6 Analysis of Safety

All safety data will be reported for the Safety population as per actual study product received. The safety profile of the study products will be assessed with respect to Exposure, AEs, incidents and OST.

Exposure is described in [Section 4.3.1](#) (Study Product Compliance and Exposure).

4.6.1 Adverse Events and Serious Adverse Events

All AEs will be reviewed by the Clinical Research Scientist or Designee prior to database lock and will be coded to a system organ class (SOC) and preferred term (PT) using the Medical Dictionary for Regulatory Activities (MedDRA).

AEs will be classified as oral and non-oral on the AE page of the electronic case report form (eCRF).

Treatment emergent adverse events (TEAEs) are defined as AEs with an onset date/time on or after the date/time of first study product use. Adverse events with an onset date/time prior to the first study product use will be considered as non-treatment emergent.

The following summary tables and listings will be presented by study product group:

- Table of treatment-emergent AEs by system organ class (SOC) and Preferred Term (PT) ([Table 14.3.1.1.1](#)). Summary of the number and percentage of subjects with at least one AE, total number of AEs, number and percentage of AEs within each SOC and PT will be displayed.
- Table of treatment-emergent AEs by Oral/Non-Oral and PT ([Table 14.3.1.1.2](#))
- Table of related treatment-emergent AEs by Oral/Non-Oral and PT ([Table 14.3.1.1.3](#))
- Listing of all AEs ([Listing 16.2.7.1](#) for all randomized subjects; [Listing 16.2.7.2](#) for non-randomized subjects)
- Listing of incidents ([Listing 16.2.7.3](#))
- Listing of deaths ([Listing 14.3.2.1](#))
- Listing of non-fatal SAEs ([Listing 14.3.2.2](#))
- Listing of treatment-emergent AEs leading to study or drug discontinuation ([Listing 14.3.2.3](#))
- Listing of treatment-emergent AEs classified as oral ([Listing 14.3.2.4](#))

In the event that there is nothing to report, a null table or listing will be produced.

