12.2.7 Safety Analysis(es)

Safety variables will focus on: -

Exposure

AEs

OST

Incidents

All AEs will be coded using MedDRA. AEs will be categorised as oral and non-oral by the primary investigator. Treatment-emergent adverse events (Oral AEs as well as all AEs) will be associated with the most recent treatment received. The number of AEs and number of subjects with AEs will be listed and tabulated by treatment. The results of OST exams will be tabulated. Incidents will be listed.

Exposure to treatment is covered under treatment compliance and the number of brushings.

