1.2 Study Objectives

The study objectives are as follows:

Objective(s)	Endpoint(s)
Primary	
To evaluate the clinical efficacy of a 0.454% SnF ₂ dentifrice in reducing gingivitis (following dental prophylaxis), as measured by the Bleeding Index (BI), compared to a negative control dentifrice, when used twice daily for 3 weeks.	Mean BI at Week 3
Secondary	
To evaluate the clinical efficacy of a 0.454% SnF ₂ dentifrice in reducing gingivitis (following dental prophylaxis), as measured by the BI compared to a negative control dentifrice, when used twice daily for 2 weeks.	Mean BI at Week 2
To evaluate the clinical efficacy of a 0.454% SnF ₂ dentifrice in reducing gingivitis (following dental prophylaxis), as measured by the number of bleeding sites (NBS), compared to a negative control dentifrice, when used twice daily for 2 and 3 weeks.	Mean NBS at Week 2 and Week 3
To evaluate the clinical efficacy of a 0.454% SnF ₂ dentifrice in reducing gingival inflammation (following dental prophylaxis), as measured by the Modified Gingival Index (MGI), compared to a negative control dentifrice, when used twice daily for 2 and 3 weeks.	Mean MGI at Week 2 and Week 3
To evaluate the clinical efficacy of a 0.454% SnF ₂ dentifrice in reducing supra-gingival plaque formation (following dental prophylaxis) as measured by the Turesky modification of the Quigley & Hein plaque index (TPI), compared to a negative control dentifrice, when used twice daily for 2 and 3 weeks.	Mean TPI (overall and interproximal) at Week 2 and Week 3
Safety	
To assess the safety and tolerability of a 0.454% SnF ₂ dentifrice when used twice daily over 3 weeks.	Treatment emergent adverse events

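### SAP 4.6.1 specifies event-based percentages with no denominator in the SOC and PT rows of the main adverse event table, where subject incidence is needed

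*SAP*

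**What the plan says.** SAP 1.2 makes treatment-emergent adverse events the endpoint of the only safety objective: "To assess the safety and tolerability of a 0.454% SnF ₂ dentifrice when used twice daily over 3 weeks". SAP 4.6 fixes the population: "All safety data will be reported for the Safety population as per actual study product received".

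SAP 4.6.1 then describes Table 14.3.1.1.1, by study product group, SOC and PT, in one sentence. It begins "Summary of the number and percentage of subjects with at least one AE" and continues "total number of AEs, number and percentage of AEs within each SOC and PT will be displayed". No denominator is given for the second percentage.

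Two further tables are named by title only, with no statistics described: "Table of treatment-emergent AEs by Oral/Non-Oral and PT" (Table 14.3.1.1.2) and "Table of related treatment-emergent AEs by Oral/Non-Oral and PT" (Table 14.3.1.1.3). All AEs are also listed, in Listing 16.2.7.1 "for all randomized subjects; [Listing 16.2.7.2](#) for non-randomized subjects", and treatment-emergent oral AEs have their own Listing 14.3.2.4.

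The corresponding protocol text, section 12.2.7, reads: "The number of AEs and number of subjects with AEs will be listed and tabulated by treatment". It names no SOC or PT level.

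**The concern.** The usual question for a safety table is what share of exposed subjects in each arm had a given event. The SAP sentence uses subjects as its unit for the overall line and changes to AEs for the SOC and PT rows. A programmer who follows it as written would produce event counts and event percentages in those rows, and no row-level subject incidence.

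The difference between events and subjects can matter here because one subject can contribute several events. Protocol 9.3.1 and 9.3.2 record any change from Screening in the hard or soft tissue examination as an AE. The soft tissue examination is repeated at Baseline, Week 2 and Week 3, and diary comments can also become AEs (protocol 8.2.4).

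What is at stake is how the trial's only safety endpoint reads. Depending on the denominator chosen, the printed percentages could suggest a difference where subject risk is equal, or hide one where it is not.

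**Working it through.** The plan states no figure on this point, so there is nothing to reproduce. The check compares what each possible percentage measures.

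**Inputs.** The planned arm size is 65 (SAP 1.1), used as the Safety population N on the assumption that every randomized subject takes at least one dose. The documents give no AE rates, so all event counts below are assumed.

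**Three candidate percentages for one SOC or PT row:**

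- Subject incidence = subjects with at least one such event / Safety N.
- Event share = events in the row / all AEs in the arm.
- Events over N = events in the row / Safety N.

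**Event share against incidence**, with one event per affected subject:

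| Case | Incidence, arm A vs B | Total AEs, A vs B | Event share, A vs B |
|---|---|---|---|
| 1 | 5/65 = 7.7% vs 5/65 = 7.7% | 20 vs 10 | 5/20 = 25% vs 5/10 = 50% |
| 2 | 6/65 = 9.2% vs 3/65 = 4.6% | 12 vs 6 | 6/12 = 50% vs 3/6 = 50% |
| 3 | 6/65 = 9.2% vs 3/65 = 4.6% | 30 vs 10 | 6/30 = 20% vs 3/10 = 30% |

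Case 1 shows a two-fold difference where the incidence is identical. Case 2 shows none where one arm has twice the incidence. Case 3 reverses the direction. In each case the cause is the number of other, unrelated events in the denominator.

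**Events over N.** Suppose an arm has six events of one PT. The percentage is 6/65 = 9.2% whether they come from six subjects (incidence 6/65 = 9.2%) or from one subject with a recurrent complaint (incidence 1/65 = 1.5%).

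Neither literal reading therefore gives subject incidence in general. Events over N equals it only when no subject has a repeat event in the row.

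**SAP against protocol.** Protocol 12.2.7 asks for two things by treatment: the number of AEs and the number of subjects with AEs. SAP 4.6.1 supplies both for the table as a whole, in the total number of AEs and in the line for subjects with at least one AE. On the overall count the two documents agree.

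**The case against.** The strongest reply is that this is loose drafting and that little turns on it. The table is defined by SOC and PT, so the qualifier at the end of the sentence could be meant to cover every item in the list, including subjects. Elsewhere the SAP bases its percentages on subjects: section 4.1.1 on the number screened or randomized, section 4.2.1 on subjects for categorical variables. The list of data displays is not legible in the supplied text, so the layout cannot be checked. Even on the literal reading, event counts are printed beside the percentages. In case 1 a reader would see 5 against 5 events, with totals of 20 and 10. Subjects per PT can be counted from the listings in a trial of about 130 subjects. No safety hypothesis is tested, and success rests only on the Week 3 Bleeding Index.

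Most of this stands, and it sets the severity. It does not remove the point. The sentence names its counting unit and distinguishes subjects from AEs, so only a non-literal reading yields incidence, and a reader should not have to rebuild the main safety result from a listing.

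A reader might go further and infer three things that the documents do not support:

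- *The protocol's count of subjects with AEs has been lost.* It has not: the overall line keeps it, and the protocol sets no SOC or PT level.
- *The arms cannot be compared.* That is too strong. It applies to percentages taken over total AEs. Event counts set against arm size remain comparable as events per subject.
- *The oral and related-event tables will also use event percentages.* Their statistics are simply not stated.

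**Conclusion.** The point holds as a low-severity correction to a descriptive safety display. As written, SAP 4.6.1 calls for event-based percentages in the SOC and PT rows, gives no denominator, and guarantees subject incidence only overall. An event-based percentage can hide, create or reverse a difference in subject incidence if taken over total AEs, and it counts repeat events if taken over the Safety population.

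The sizes shown rest on assumed counts and on 65 dosed subjects per arm. They show what could happen and do not estimate anything in this trial. The verdict also rests on the literal reading. If the sponsor already intended subjects, the change only confirms that. No figure in the documents is wrong, and the primary analysis is untouched.

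**What to change.** In SAP 4.6.1, replace the description of the SOC and PT rows of Table 14.3.1.1.1 with wording to this effect: each SOC and PT row shows the number and percentage of subjects with at least one event, with the Safety population N for that study product as denominator and each subject counted once per SOC and once per PT; the number of events is shown alongside. State that Tables 14.3.1.1.2 and 14.3.1.1.3 use the same layout, with subjects counted once per oral/non-oral category and once per PT.

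The cost is one sentence in the SAP and a check of three table shells. No data collection, sample size or efficacy analysis changes, and the wording is consistent with protocol 12.2.7, so no protocol amendment is needed.

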4.6.2 Other Safety Variables

A shift table of OST by examination will be provided, for each of the study products ([Table 14.3.4.1](#)) comparing baseline results to post-baseline results at Week 2 and Week 3, for the Safety population.

Oral soft tissue (OST) and oral hard tissue examination (OHT) data will be listed ([Listing 16.2.9.1](#) and [Listing 16.2.9.2](#) respectively) for all randomized subjects.

4.7 Analysis of Other Variables

Repeat MGI and TPI assessments will be performed by the clinical examiner at Baseline (Visit 2), Week 2 (Visit 3) and Week 3 (Visit 4). At least 2 repeat assessments should be performed for each index on each clinical assessment day (≥ 1 in the morning; ≥ 1 in the afternoon). ‘Repeat’ subjects will be selected at random from those in attendance. Different subjects can be used for repeat MGI and TPI assessments.

The repeat dental assessments (MGI and TPI) will be compared to the original assessments and will be used to investigate intra-examiner variability. The repeat assessments will not be used in any efficacy analyses..

The first and repeat assessments for each tooth site will be cross tabulated for MGI ([Table 14.2.7.1](#)) and for TPI ([Table 14.2.7.2](#)).

A weighted Kappa coefficient (κ), along with the 95% CI will be calculated to assess the intra-examiner reliability. Fleiss-Cohen weighted kappa will be calculated for the repeatability analysis. Reliability will be deemed:

Stannous Fluoride

Protocol Number: 212537

Statistical Reporting and Analysis Plan Text, Amendment 1, Final V1.0, 04 Oct 2019

- Excellent if $\kappa > 0.75$
- Fair to good if $0.4 \leq \kappa \leq 0.75$
- Poor if $\kappa < 0.4$

This analysis will be conducted for MGI using the MGI Repeatability population and for TPI using the TPI Repeatability population.

5 Changes to the Protocol Defined Statistical Analysis Plan

There were no changes or deviations to the originally planned statistical analysis specified in the protocol, dated 22-Jun-2019 and protocol administrative change letter, dated 11-Sep-2019.

Attachment 1: List of Data Displays

212537 (CCI) [Redacted]
Gingivitis) List of TFLs
